10 FEB 2015

# **1 INTRODUCTION**

This document serves as an addendum to the finalized Statistical Analysis Plan. It describes minor additions to the analyses, and clarifies aspects of the earlier text.

## 2 CHANGES TO THE SPECIFIED ANALYSES

The following changes will be made:

#### 2.1 Adverse Event Classification

Adverse events will be classified using MedDRA v16.0 in conjunction with investigator evaluation of the etiology of the adverse event. Each event will be classified as one of the following:

- Symptom of allergic reaction (allergy)
- Symptom of allergic reaction to food (food allergy)
- Non-allergic symptom, alternate etiology known
- Non-allergic symptom, alternate etiology not known
- Unable to classify symptoms as either allergic or non-allergic.

Flags for each of those classifications will be added to the AE listings.

Events classified as allergies or food allergies will be classified as having system organ class (SOC) = 'IMMUNE SYSTEM DISORDERS', preferred term (PT) = 'HYPERSENSITIVITY', and lower level term = 'ALLERGIC REACTION'. Those events will be further classified by specific system organ class and preferred term of the allergy (for instance, vomiting would have specific SOC = 'GASTROINTESTINAL DISORDERS' and PT='VOMITING', as per MedDRA).

In addition to the original summary tables, additional summary tables of hypersensitivity adverse events, by specific classification, will be presented.

Table and listing footnotes will be updated as appropriate.

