#### 7.8 Randomization, Treatment Assignments, and Blinding

Subjects are randomized in a 1:1 ratio to each study treatment (CPNA or placebo) using the TEMPO system. A central randomization schedule of randomly permuted blocks was prepared by an independent unblinded statistician for use in the TEMPO system.

Subjects will be unblinded after the final visit is completed and they exit the ARC001 trial. Subjects who withdraw and do not complete their final visit assessments will be unblinded after they exit from the study. End of study (scheduled) unblinding will be requested by the site. Emergency (unscheduled) unblinding for safety reasons may also occur, as described in the protocol. Emergency unblinding may be requested by the site or other study team members (such as the medical monitor).

For either type of unblinding, the date of unblinding, type (scheduled or unscheduled), and person who requested the unblinding will be processed and documented in TEMPO. The actual treatment assignment will be made available only to the person requesting unblinding. Other study team personnel will receive notification that the treatment assignment has been provided, but will not be notified of the actual treatment assignment.

Masking procedures for outputs provided only to the Data Monitoring Committee (DMC) are described in the DMC Charter.

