## **10.3** Adverse Events

All reported adverse events (AEs) will be classified into System Organ Class (SOC) and Preferred Term (PT) using Medical Dictionary for Regulatory Activities (MedDRA) version 16.0. A summary of SOC, PT, and verbatim term will be provided.

Treatment-emergent adverse events (TEAEs) are defined as any event starting during or after the active treatment period. Any event occurring on the same day as a DBPCFC or in-clinic escalation dosing will be considered to be associated with those events, and flagged as such in the listings. Events will be classified by onset time with regards to time of last dose (within 2 hours of last dose, > 2 hours since last dose, and unknown time since last dose).

Events will be further classified by time period of onset, as follows:

- *Pre-study*: All events beginning prior to first dose of Screening DBPCFC; if times are unavailable, any event prior to the first day of Screening DBPCFC.
- Screening DBPCFC: All events beginning after the first dose of the food challenge during the Screening DBPCFC, and within 24 hours of the last dose of that food challenge and prior to the first dose of randomized treatment. If times are not available, any event starting on the same day as any part of the Screening DBPCFC will be categorized as Screening DBPCFC.
- Pre-treatment: All events beginning more than 24 hours after the last dose of the Screening DBPCFC but before the first dose of randomized treatment. If the two halves of the food challenge are more than 24 hours apart, events that begin more than 24 hours after the end of the first half, but prior to the start of the second half, will be categorized as Pre-treatment. If times are not present, events beginning on any day after the first day of Screening DBPCFC, and before Visit 01 Day 1, excluding any day on which Screening DBPCFC is administered, will be Pre-treatment.
- Visit 01: All events beginning on or after the first dose on Visit 01 Day 1, and within 24 hours of the last dose administered at Visit 01 (Days 1, 2, or 3); if times not present, events beginning on the same date as any day of Visit 01.
- *Up-dosing Visit*: All events beginning on or after the increased dose administered and within 24 hours of that dose; if times not present, events

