Listings will be provided for all adverse events; serious adverse events (SAEs); severe, life-threatening, or fatal adverse events; adverse events leading to death; adverse events leading to permanent withdrawal of study treatment; adverse events related to study treatment; and adverse events occurring within 2 hours of the last dose of randomized study treatment. Listings of both adverse events associated with DBPCFC, and SAEs associated with DBPCFC, will be provided. A separate listing of all adverse events, sorted by time period of onset, will also be provided; and SAEs will be flagged.

An overall summary of frequencies of types of adverse events (TEAEs, SAEs, etc.) will be provided. An additional summary table of all TEAEs by Preferred Term, in order of descending frequency, will also be provided.

Summaries of adverse events by time period, SOC, and PT will be provided for TEAEs, treatment-emergent SAEs, and TEAEs related to study treatment. Subjects will be counted at most one time per time period overall, at most one time per SOC and at most one time per PT for these summaries. Summary tables will be sorted in order of time period (overall, then chronological), descending overall frequency of SOC and PT, with alphabetical sorting for ties. The number of subjects at risk for each time period (i.e., the number of subjects on study at the beginning of each time period) will be used as the denominator. In other words, the number of subjects in the Safety population will be used as the denominator for the Overall, On-treatment, and Post-Treatment time periods, the number of subjects undergoing Visit 01 will be used as the denominator for Visit 01, the number of subjects with 1+ updosing visits will be used as the denominator for Updosing Visit, the number of subjects undergoing the Exit DBPCFC will be used as the denominator for the Exit DBPCFC, Post-Exit DBPCFC time points.

Events related to study treatment are defined as those classified as possibly, probably, or definitely related to study treatment. If relationship is missing, the event will be conservatively be summarized as being related to study treatment.

Event severity is classified as mild, moderate, severe, life-threatening, or death. If severity is missing, a separate category of missing severity will be included in the summary table, and no imputation of severity will be performed.

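### As SAP Addendum 2.1 reads, each symptom's adverse events are split between the main and the added tables, so no planned adverse-event table gives any-cause symptom incidence by arm

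*SAP*

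**What the plan says.** SAP Section 10.3 sets the base rule: "All reported adverse events (AEs) will be classified into System Organ Class (SOC) and Preferred Term (PT") under MedDRA 16.0. The main tables are built on that coding: "Summaries of adverse events by time period, SOC, and PT will be provided for TEAEs, treatment-emergent SAEs, and TEAEs related to study treatment". Further tables break TEAEs down by timing relative to the last dose and by severity, and one lists them by preferred term alone (Tables 14.3.1.2 to 14.3.1.7). In the summaries by time period, SOC and PT, subjects are counted "at most one time per SOC and at most one time per PT for these summaries".

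SAP Addendum 2.1, under the heading for changes to the specified analyses, sorts every adverse event into one of five etiology classes. It does so using MedDRA "in conjunction with investigator evaluation of the etiology of the adverse event". For the two allergic classes, the events judged to be "allergies or food allergies will be classified as having system organ class (SOC) = 'IMMUNE SYSTEM DISORDERS', preferred term (PT) = 'HYPERSENSITIVITY". The symptom is kept as a second code: "Those events will be further classified by specific system organ class and preferred term of the allergy". The original tables stay, and "additional summary tables of hypersensitivity adverse events, by specific classification, will be presented". Classification flags go into the listings, and footnotes are to be updated.

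**The concern.** Safety, measured by the incidence of adverse events and dosing symptoms, is the first secondary objective (Protocol 2.2, SAP 2.1.2). A reader will look up a symptom such as vomiting and compare the arms. Under the addendum that row depends on an etiology judgement. Events called allergic leave it, while events called non-allergic or unclassifiable stay. SOC rows are split in the same way, because the SOC is reassigned along with the preferred term.

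Protocol 1.6.1 expects peanut dosing to cause allergic symptoms, and its list includes nausea, vomiting, abdominal discomfort and cough. These also occur for other reasons. The judgement that moves events out of the symptom rows is therefore expected to be made more often on CPNA. If so, the main rows understate symptoms most in the arm whose safety is in question.

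**Working it through.** The plan states no figure to reproduce. The check is whether any-cause incidence can be recovered from the planned tables.

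**Where a vomiting event appears**

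| Etiology class | Main tables (14.3.1.2 to 14.3.1.7) | Added tables |
|---|---|---|
| Allergy or food allergy | Hypersensitivity row | Vomiting row |
| Non-allergic, other cause known or not known | Vomiting row | Absent |
| Unable to classify | Vomiting row | Absent |

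No planned adverse-event table has a Vomiting row containing all the classes.

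**What two separate rows can tell the reader.** In an arm of n subjects, let a be the number with at least one allergic vomiting event (added table) and b the number with at least one other vomiting event (main table). A subject may be in both. The number U with vomiting from any cause satisfies

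max(a, b) ≤ U ≤ min(n, a + b).

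The main row shows b, so it falls short by U − b, which lies between max(0, a − b) and min(a, n − b).

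**Illustration.** The arm size is n = 25, from about 50 subjects randomized 1:1 (SAP Section 4). All counts a and b are assumed, because the documents give none by arm. Each pair of values is CPNA, then placebo.

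| Case | a | b | Main row | Any-cause CPNA | Any-cause placebo | Any-cause difference (points) |
|---|---|---|---|---|---|---|
| A | 10, 2 | 4, 4 | 16%, 16% | 40 to 56% | 16 to 24% | +16 to +40 |
| B | 8, 2 | 2, 8 | 8%, 32% | 32 to 40% | 32 to 40% | −8 to +8 |
| C | 5, 3 | 4, 4 | 16%, 16% | 20 to 36% | 16 to 28% | −8 to +20 |
| D | 3, 3 | 4, 4 | 16%, 16% | 16 to 28% | 16 to 28% | −12 to +12 |

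Case A in full:
- CPNA: max(10, 4) = 10 and 10 + 4 = 14, so 10/25 = 40% to 14/25 = 56%.
- Placebo: max(2, 4) = 4 and 2 + 4 = 6, so 16% to 24%.
- Difference: from 40 − 24 = 16 to 56 − 16 = 40 points.
- Shortfall of the main row: 6 to 10 subjects on CPNA (24 to 40 points) and 0 to 2 on placebo (0 to 8 points).

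Cases A, C and D show the same main row, 16% in both arms, although the any-cause differences behind it are not the same. In case D, with no imbalance in allergic calls, each row is short by 0 to 3 subjects (0 to 12 points), with the same bounds in both arms.

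**Whether other tables fill the gap.** Tables 14.3.4.1, 14.3.4.3 and 14.3.4.4 count pre-specified symptoms, including vomiting, whatever their cause. They cover only the food challenges and the in-clinic escalation doses (SAP 10.5, 10.6). At-home dosing symptoms are summarized only as the number of days with any symptom (SAP 10.7), although Protocol 7.6 names the home symptom logs as a source of adverse events. Outside clinic sessions, the adverse-event tables are the only planned summary by symptom.

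**The case against.** The other side has several fair points.

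- **The symptom code is kept.** A reader might infer that the recoding destroys the symptom information. It does not: the specific SOC and preferred term are retained, and the pooled count can be programmed. What is missing is a planned table that does it.
- **The addendum does not state that the original tables use the reassigned term.** This is correct, and it calls itself a set of minor additions and clarifications. But Section 10.3 builds the tables on the term into which an event is classified, and the addendum changes that classification. Symptom tables for hypersensitivity events alone would be of most use if the main tables no longer show those symptoms. The sponsor should state which is meant.
- **Symptom incidence is shown elsewhere.** This is true for challenges and clinic doses, so it would be wrong to say that it appears nowhere.
- **Some allergic symptoms never reach the adverse-event form.** Protocol 7.1 sends dosing symptoms to the dosing form, and non-serious challenge and accidental-exposure reactions to other forms. This limits how much the main rows lose, by an unknown amount.
- **No event disappears.** Total TEAE and SAE counts stand, and moved events appear in the Hypersensitivity row. If no subject had both kinds of event, the two rows would add exactly. The tables do not show whether that is so.
- **Anaphylaxis has its own episode summary (Table 14.3.3.1).** The addendum's classes are worded for symptoms, and it does not say how an anaphylaxis diagnosis is coded. If it is recoded, the SAE table would not show it under its own term, and the episode table does not change that.

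A reader might also infer that the etiology call was made after unblinding, since "End of study (scheduled) unblinding will be requested by the site" as each subject finishes. The documents do not say when the call was made. Protocol 7.5.1 and 7.6.2 place causality with the site investigator as part of adverse-event assessment and reporting, so this inference is not supported.

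**Conclusion.** The gap in the planned tables is real on the natural reading of Addendum 2.1. For adverse events outside clinic sessions, any-cause symptom incidence by arm would be known only between max(a, b) and min(n, a + b). The main symptom rows would be lowered most in the arm with more allergic calls.

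That this arm is CPNA is an inference from Protocol 1.6.1. Protocol 1.2 reports that earlier symptoms occurred in both arms and gives no rates. The size is therefore unknown, and the worked cases show only what is possible. A reader might conclude that the main rows will reverse the direction of a symptom difference. That depends wholly on assumed rates and is not established. The point concerns the reading of individual safety terms. It does not touch efficacy or the overall event counts, but it is worth correcting because the correction is small.

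**What to change.** In SAP Addendum 2.1:

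1. Add summaries of TEAEs and of treatment-emergent SAEs by arm that use the specific (native MedDRA) SOC and preferred term for every event, whatever its allergic class, with anaphylaxis under its own preferred term.
2. Keep the Hypersensitivity grouping and the added hypersensitivity tables, described as subsets of these summaries.
3. Footnote Tables 14.3.1.2 to 14.3.1.7 to say that their symptom rows exclude events classed as allergic. If the sponsor meant those tables to stay on native coding, one sentence saying so would do the work of items 1 and 3.

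The cost is a few more table pages and modest programming on retained variables. No new data are needed, and the investigators' etiology classification can stay as it is.

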# 2.2 Completer Population

An additional analysis population will be added. The Completer population will include all subjects in the mITT population who were eligible for the Exit DBPCFC. Exclusions from this analysis population will be reviewed at the pre-DBL determination meeting as described in Section 12 of the SAP.

Efficacy tables currently being produced on the ITT, mITT, and PP populations will also be produced on the Completer population.

# **2.3 Study Product Administered After Exit DBPCFC**

In some cases, study product was administered following Exit DBPCFC, to allow subjects to continue to receive product prior to rolling over to the ARC002 study. Subjects remained enrolled in the ARC001 study during this time, and recorded study product in the daily diary.

This post-Exit DBPCFC study product will be excluded from summaries of exposure and compliance, and footnoted as such. Disposition listings reflecting the date of last study treatment will be flagged to indicate where study treatment was taken after Exit DBPCFC.

#### 2.4 Clarifications to original text

- An unsuccessful dose increase is defined as a single dose at a higher dose level, followed by a return to the previous dose level (or a lower level).
- A dose reduction is any decrease in dose level that does not qualify as an unsuccessful dose increase.
- When calculating dose compliance, a "partial" dose will be calculated as 50% of the planned dose amount.
- The initial escalation kit used for Visit 01 is not tracked as part of drug accountability in TEMPO.
- Average daily dose will not be listed by time period.
